Cost effectiveness is an important issue and while combination of IVIG and rituximab has been advocated, the cost of such treatment is substantial and whether it poses any benefit over rituximab alone, or with other more conventional immunosuppressive agents, has not been established. Both treatment approaches have been previously published in high impact journals.^{3,5} In this study, we aim to evaluate the efficacy and safety of early use of rituximab with or without IVIG in patients with moderate to severe pemphigus using protocols that were similar to those previously published. Apart from complete remission and adverse effects, we will also aim to measure the impact of health care economics and in doing so, assess the cost and benefits of both treatment arms.

Hypothesis:

IVIg in combination with Rituximab is more superior than Rituximab alone in the treatment of moderate to severe pemphigus.

Methods:

Prospective multi-centre, randomised open-label trial

Patients will be randomised to two treatment arms: Rituximab alone or Rituximab + IVIG

Aim to recruit ~10 patients per arm (20 patients in total)

Patients will be reviewed monthly for the first 6 months then 3 monthly in clinic thereafter, follow up will be up to 4 years.

When patient enrolment is confirmed and written consent is obtained, the investigator will open the envelop sequentially and patient will receive the treatment plan stated on the allocation slip. Patient will be randomised to either rituximab arm or rituximab and IVIG arm. The random allocation sequence will be generated using computer-generated random numbers. Randomisation will be to the two arms of the trial in 1:1 ratio. The allocation sequence will be printed on paper slip. A non-study related research assistant will put the slips in to sequentially numbered, opaque, sealed envelopes.

Arm 1 (Rituximab alone arm):

- Rituximab infusion 375mg/m² body surface area (BSA) weekly for 4 weeks from baseline
- Rituximab infusion 375mg/m² BSA weekly for 4 weeks at week 24
- Rituximab infusion 375mg/m² BSA weekly for 4 weeks at week 52
- A total of 12 doses of rituximab will be given in 55 weeks
- If a patient relapses after initial rituximab infusion, further rituximab infusion 375mg/m² BSA weekly for 4 weeks can be given at time of relapse/or if patient fails to achieve complete remission 2 months from last dose of rituximab.

Week 0, 1, 2, 3	Rituximab (375mg/m ²)
Week 24, 25, 26, 27	Rituximab (375mg/m ²)
Week 52, 53	Rituximab (375mg/m ²)
Week 76, 77	Rituximab (375mg/m ²)

Arm 2: (Rituximab and IVIG arm):⁵

- Rituximab (375 mg/m² BSA) once a week for 4 weeks (week 1, 2, 3) and
- Week 4: Rituximab + IVIG 2g per kg
- Week 5, 6, 7: Above treatment repeated for 2nd cycle, infusion of rituximab (375 mg/m² BSA) once a week for 4 weeks (week 5, 6, 7) and
- Week 8: Rituximab + IVIG 2g/kg
- In week 12, 16, 20, 24 patients received a single infusion of rituximab (375 mg/m² BSA) plus infusion of 2g/kg IVIG
- Thus in 24 week period patients received a total of 12 infusions of rituximab and 7 infusions of IVIG
- If a patient was clinically free of disease at end of 24 weeks, additional infusions of IVIG will be given at week 30, 38, 48, 60 and 76
- A total of 12 doses of rituximab will be given and 12 cycles of IVIG will be given
- If a patient relapses or flares during the treatment, four infusions of rituximab at 375mg/m² BSA will be given at 1-weekly interval will be administered and IVIG 2g/kg will be given at week 4 of treatment after week 32

Week 0	IVIG 2g/kg, divided total dose given over 2-5 days
Week 1, 2, 3	Rituximab (375mg/m ²)
Week 4	Rituximab (375mg/m ²) + IVIG
Week 5, 6, 7,	Rituximab (375mg/m ²)
Week 8	Rituximab (375mg/m ²) + IVIG
Week 12	Rituximab (375mg/m ²) + IVIG
Week 16	Rituximab (375mg/m ²) + IVIG
Week 20	Rituximab (375mg/m ²) + IVIG
Week 24	Rituximab (375mg/m ²) + IVIG
Week 30	IVIG
Week 38	IVIG
Week 48	IVIG
Week 60	IVIG
Week 76	IVIG

For both study arms:

- After initial induction phase for both arms, the time between subsequent doses of rituximab for treatment of relapse should be at least 2 months apart.
- Patients will be followed up for 4 years starting from baseline visit

IVIG and Rituximab

Ahmed et al.⁵⁻⁷ has published data and protocol combining rituximab and IVIG. The theory behind this is that IVIG:

- Contains antibodies directed against B-cell-activating factor belonging to tumour necrosis factor family
- Exact mechanism by which Rituximab and IVIG are effective in induction of prolonged sustained clinical, serological and immuno-pathological remission in patients is not clearly understood – After destroying autoantibody-producing pathogenic B cells, the repopulating B cells do not produce autoantibodies. It is conceivable that in a microenvironment that more closely resembles normal physiology and homeostasis, IVIG could initiate the process of immune restoration.

Current practice/treatment in local hospital (IVIG +Rituximab) and existing side effects

IVIG and rituximab combination therapy has not been used in local hospitals for the treatment of pemphigus. This is a pilot study in Hong Kong comparing the use of combination therapy with IVIG and Rituximab versus rituximab alone in the treatment of pemphigus. Ahmad *et al.*⁸ found that combination therapy with IVIG and rituximab in 10 patients with pemphigus with contraindications to systemic corticosteroid resulted in long-term sustained remission (> 6 years). Of note there were lack of adverse events, no infections, deaths or hospitalisations.

Criteria:

Ages Eligible for study : 18 years to 70 years (Adult, Older Adult), by the day of signing informed consent

Sexes Eligible for study : All

Inclusion Criteria:

- Written informed consent obtained from patient
- Ages Eligible for Study: 18 years to 70 years (Adult, Older Adult)
- Newly or recently diagnosed (less than 18 months) diagnosed pemphigus vulgaris or pemphigus foliaceus based on clinical features; histological features of acantholysis via skin or mucosal biopsy; and intercellular staining pattern of indirect immunofluorescence or serological detection of DSG 1 or DSG 3 by enzyme-linked immunosorbent assay (ELISA)
- Moderate to severe active disease, as defined by overall PDAI \geq 15 or skin involvement BSA \geq 5%.⁹ [Annex 1]
- Receiving standard-of-care oral prednisolone up to 1.5 mg/kg/day
- Women who are sexually active and not postmenopausal, agreement to remain abstinent or use 2 effective methods of contraception.
- Ability to comply with study protocol as deemed by investigator's assessment

Exclusion criteria:

- Age <18 or >70
- Pregnant women or nursing mother
- Already diagnosed pemphigus patients diagnosed > 18 months
- Non-consenting patients, or patient who cannot be followed up regularly
- Patient with history of serious allergy or anaphylactic reaction to monoclonal antibody treatment
- Severe heart failure (NYHA Class III or IV)
- Unstable angina or myocardial infarction within last 3 months or post-infarction heart failure
- Anaemia (haemoglobin $<10\text{g/dL}$), Neutropenia ($<1000/\text{mm}^3$), Lymphopenia ($<900/\text{mm}^3$), thrombocytopenia ($<100,000/\text{mm}^3$)
- Renal insufficiency eGFR <60
- Liver insufficiency of ALT/AST > 2 times normal limit range
- Positive test results for hepatitis C (HCV) serology at screening
- Blood test positive for HIV
- Signs of active infection on CXR
- Positive interferon gamma release assay Quantiferon or T.Spot TB test: must be treated with at least 4 weeks post initiation of isoniazid or other TB therapy
- Inherited or acquired severe immunodeficiency
- History of malignancy
- Patient with active severe infection (excluding fungal infections of the nail), which has required antibiotic treatment within 2 week prior to study enrolment
- Infection requiring hospitalisation or intravenous antibiotic treatment within the last 8 weeks prior to enrolment

- Past history of osteomyelitis, or fasciitis, septic arthritis within the last one year
- Patients with drug induced pemphigus. A thorough medication history will be taken to rule out drug induced pemphigus including D-penicillamine, angiotensin-converting enzyme inhibitors, angiotensin receptor blockers and cephalosporins
- Evidence of any new or uncontrolled concomitant disease that in the investigators' judgement would preclude the patients participation
- Patients with history of allergy or adverse events to IVIG or rituximab treatment¹⁰
- Treatment with intravenous immunoglobulins, plasmaphoresis within the last 8 weeks prior to randomization
- Previous treatment with rituximab or any monoclonal antibody inducing profound lymphopenia
- Treatment with live or attenuated vaccine within the last 28 days prior to randomization

Admission and follow up:

- All infusions will be performed as in-patient procedure of prospective hospital and all patients are to be follow up monthly at out-patient of the prospective Queen Mary Hospital dermatology out-patient clinic
- Patients will be followed up monthly for the first 6 months, then followed up for every 3 months up to 4 years starting from baseline visit

Outcome measures:

Patients' serum will also be taken for desmoglein antibodies and levels will be charted and independent samples t-test will be used to compare the collected data between the two groups. Homogeneity of the treatment groups at baseline will be analyzed using the Mann–Whitney U test and Wilcoxon signed-rank test for independent and dependent variables. The Kaplan-Meier method will be used to estimate the likelihood of reaching the endpoint of relapses or flares within the drug infusing period based on the intention-to-treat population, defined as all patients who has received at least one dose of study medication. The log-rank test will be used to compare time-to-event curves between treatment groups.

Statistical analysis of results will be done with IBM SPSS statistic program version 25. All tests of significance are two-tailed, and a P value of < 0.05 is considered to indicate statistical significance.

Primary outcome:

- 1) Percentage of participants who achieve relapse-free complete remission

Secondary Outcomes:

- 2) Time to protocol defined disease flare
- 3) Duration of complete remission, evaluated by the PDAI activity score [Baseline up to end of study]
- 4) Number of protocol defined disease flares
- 5) Time to initial complete remission, evaluated by the PDAI activity score [Baseline up to end of study]
- 6) Change in health-related quality of life as measured by the Dermatology Life Quality Index (DLQI) Score [Time Frame: Baseline, Week 4, 12, 24, 36, 48, 60, 72, 84, 96, 120, 144, 168, 192]
- 7) Occurrence of severe treatment adverse events (grade 3 or 4) based on common terminology criteria for adverse events (CTCAE), or death from any cause
- 8) Blood DSG 1 and 3 levels [Baseline week 0, week 4, 12, 20, 24, 36, 48, 60, 72, 96, 120, 144, 168, 192]
- 9) Blood lymphocyte level (CBC) [Baseline week 0, week 4, 12, 24, 36, 48, 60, 72, 96, 120, 144, 168, 192]
- 10) Blood CD19/20 mean B cell counts percentage [Time Frame: Baseline, week 4, 12, 20, 24, 36, 48, 60, 72, 96, 120, 144, 168, 180, 192]
- 11) Number of rescue therapy given

Baseline investigations prior to commencing therapy

General investigations:

- CBC
- Renal panel
- Liver panel
- Fasting Glucose/HbA1c
- Urine microscopy
- Urine pregnancy test in women of childbearing age
- Serum immunoglobulins for IgA deficiency
- B cell (CD19/20) enumeration

- DSG 1, 3 ELISA

Infective screen:

- HepBs Ag, Anti-HBs Ab, anti-HepBc total antibodies
- Anti-HCV IgG
- Anti HIV 1 and 2 (if indicated)
- CXR
- Interferon-gamma release assays

Patients who have positive IGRA test results

As Tuberculosis (TB) is endemic in Southeast Asia, should Interferon-gamma release assays result be positive, the patient will be reviewed by infectious diseases specialist and need treatment of latent TB treatment prior to starting Rituximab. Patients will need to have completed at least 4 weeks of isoniazid or treatment with other TB medications, before commencement of the study.

Patients who are HepBs Ag positive, or HepBs Ag negative and anti-HepBc Ab – positive

Viral hepatitis is a major healthcare burden especially in Hong Kong, which is considered to be part of an endemic region. The seroprevalence of anti-HepBc is estimated to be as high as 37.3%,¹¹ therefore the exclusion of HepBs Ag positive and HepBc Ab positive patients were amended in study protocol, and these patients will be included in the study.

Baseline HepB DNA levels will be done for patients who are HepBs Ag positive, and anti-hepBc Ab positive

Patients will be monitored for AST and ALT levels at least every 3 months, HepBsAg and HBV DNA tests repeated whenever clinically indicated

Patients who are HepBs Ag positive – will be started on entecavir 0.5mg daily, and will be referred to a gastroenterologist for further follow up.

Patients who are HepBs Ag negative, and HBc Ab positive, with detectable HepB DNA levels – will be started on entecavir 0.5mg daily, and will be referred to a gastroenterologist for further follow up.

Patients who are HepBs Ag negative, HBc Ab positive, with no detectable HepB DNA levels, will be started on entecavir 0.5mg daily, and will be continued on entecavir for at least 18 months after completion of last dose of rituximab.^{12,13}

Monitoring and definitions of disease outcome parameters:¹⁴

- **Control of disease activity:** Time at which new lesions cease to form and established lesions begin to heal.
- **End of consolidation phase:** Time at which no new lesions have developed for a minimum of 2 weeks and approximately 80% of lesions have healed
- **Complete remission:** The absence of new or established lesions
- **Complete remission off therapy:** The absence of new or established lesions while the patient is off all systemic therapy for at least two months.
- **Relapse/flare:** Appearance of ≥ 3 new lesions/month that do not heal spontaneously within 1 week, or by the extension of established lesions, in a patient who has achieved disease control

Steroid regimen and tapering:

Prednisolone tapering³

Severe Pemphigus (PDAI ≥ 45):⁹

- Prednisolone 1mg/kg/day for 1 month, then 0.75mg/kg/day for 1 month then 0.5mg/kg/day for 1 month, then 0.3mg/kg/day for 1 month then 0.2mg/kg/day for 1 month, then 0.1mg/kg/day for 1 month then off

Moderate pemphigus (PDAI ≥ 15):⁹

- Prednisolone 0.5mg/kg/day for 1 month, then 0.3mg/kg/day for 1 month then 0.2mg/kg/day for 1 month then off

Steroid sparing agents such as azathioprine or MMF are reduced to half the dose once the patient is successfully recruited into the study and will be tapered and stopped upon commencement of the study.

Relapse/ failure to achieve complete remission

- Additional infusion of weekly rituximab 375mg/m² BSA weekly x 4 will be given at the time of relapse/ or if patient fails to achieve complete remission 2 months from last dose of rituximab. After initial induction phase for both arms, the time between subsequent doses of rituximab for treatment of relapse should be at least 2 months apart.

Rituximab infusion protocol:

Pre-medications

- Paracetamol 1000mg one hour before Rituximab infusion
- IV Piriton 30 minutes before Rituximab infusion
- Methylprednisolone 100mg IV or Hydrocortisone 100mg IV half hour before Rituximab infusion

Preparation:

- IV Rituximab is prediluted at a dose of 500mg in 500ml of 0.9% normal saline (i.e. 1:1 dilution, 1 mg/ml)
- Initial infusion rate starts at a rate of 50mg/hr (50ml/hr)
- If no hypersensitivity/anaphylaxis reaction occurs, increase infusion rate in 50mg/hr (50 ml/hr) increments every 30 minutes

- Maximum infusion rate is 400 mg/hr (400 ml/hr)
- Subsequent infusion: start at rate of 100mg/hr (100 ml/hr), increase 100mg/hr (100 ml/hr) increments every 30 minutes
- Monitor temperature, BP HR, respiratory rate and SpO2 every 30 minutes

Adverse effects

Infusion-related:

- Fever, chills/rigors
- Injection site pain
- Nausea and vomiting
- Asthenia, headache, myalgia, giddiness
- Rhinitis, throat irritation
- Pruritus, rash
- Risk of infections
 - ** Infections including urinary tract infections, pneumonia, pneumocystic pneumonia, herpes simplex, herpes zoster, cytomegalovirus infection. Lung and brain abscess. Severe hypogammaglobulinaemia, and high-dose immunosuppressants may be possible risk factors for systemic infections
- Neutropenia
- Pyelonephritis
- Haemolytic anaemia
- Toxic epidermal necrolysis
- Parkinsonism

Intravenous immunoglobulins (IVIG)

Treatment dosage: 2g/kg over 2-5 days

Infusion Protocol

0 min	: 50ml/hour
15 min	: 75ml/hour
30 min	: 100ml/hour
45 min	: 125ml/hour
60 min	: 150ml/hour
75 min & beyond	: 180ml/hour

For patients receiving IVIG for first time, wait 30mins before 1st increase. Infusion rate should be less than 0.27ml/kg/hour in the following groups of patients:

- Renal insufficiency
- Diabetes mellitus
- ≥ 65 years of age
- Sepsis
- Paraproteinaemia
- Patients receiving nephrotoxic drugs

* In patients with renal impairment, or risk factors for thromboembolic disease or fluid overload, consider infusing IVIG at a dose of 0.4g/kg/day for 5 days (total dose 2g/kg) at a rate of less than 0.27ml/kg/hour, and in not less than 8 hours.

- Restoring immune regulation when B cells are being re-populated to normal levels
- Synergy and interactions of immune pathways and inflammatory system
- IVIG regulated B cell functions and suppression of production of pathogenic autoantibodies through idiotype network interactions

During IVIG infusion:

- Hourly parameters, watch out for tachycardia, hypertension, dyspnoea, chest tightness, facial flushing, fluid overload
- In the event of an adverse reaction:
 - Inform the doctor
 - Decrease the infusion rate to previous level or stop the infusion if symptoms persist
 - Do not increase the rate any further
 - Paracetamol for fever, chills, headache or myalgia and antihistamines for pruritus or urticaria
 - Restart at a slower rate when symptoms have resolved, and consider premedication prior to future infusions
 - Report as adverse reaction to a blood product

Anaphylactic reaction

Syncope (dizziness), dyspnoea, hypotension

- Stop the infusion immediately
- Resuscitate if necessary
- Oxygen therapy, IV antihistamines (benadryl 50mg) and other appropriate measures

Other potential adverse events:

- Acute renal failure
Elderly patients and those with diabetes mellitus or impaired renal function are at risk
- Arterial thrombosis (stroke and myocardial infarction) and venous thrombosis (deep vein thrombosis and pulmonary embolism) following IVIG have been reported. Patients at risk of thrombotic events may include those with a history of atherosclerosis, multiple cardiovascular risk factors, advanced age, impaired cardiac output, and/or known or suspected hyperviscosity.⁶
- Transmission of blood-borne agents such as Hepatitis B/C and HIV
- Acute meningitis syndrome
This may occur 48 to 72 hours after IVIG.
Signs and symptoms include severe headache, nuchal rigidity, drowsiness, fever, photophobia, nausea and vomiting.
May occur more frequently with high dose (2g/kg) IVIG treatment.

- Cutaneous reactions
Reports of eczematous reactions and other varied morphologies. One report of erythema multiforme.

The British Associate of Dermatologists guidelines for management of pemphigus vulgaris 2017 ¹

First-line therapy	
Corticosteroids
 
 - Oral prednisolone 0.5-1mg/kg - Increase 50-100% increments every 5-7 days if blistering continues - Taper dose once remission is induced and maintained - Assess risk of osteoporosis 
Combine corticosteroids with an adjuvant immunosuppressant
 
 - Rituximab (rheumatoid arthritis protocol, 2x 1g infusions, 2 weeks apart) - Azathioprine 2-3 mg/kg per day (if TPMT normal) - Mycophenolate mofetil 2-3g/day
Second-line therapy	Consider switching to alternate corticosteroid-sparing agent if treatment failure with first-line adjuvant drug (azathioprine, mycophenolate mofetil or rituximab)
Third-line therapy	Consider additional treatment options based on assessment of individual patient need and consensus of multidisciplinary team, options include: 
 - Cyclophosphamide - IVIG - Methotrexate - Plasmapheresis or plasma exchange

Additional management for oral pemphigus

- Topical analgesics or anaesthetics (e.g. viscous lidocaine 2% solution, lidocaine 2% gel, difflam gargle) are useful particularly prior to eating or toothbrushing
- Topical medium or high potency corticosteroids (e.g. triamcinolone acetonide 0.1% in adhesive paste, clobetasol propionate) applied directly to the lesions, corticosteroid mouthwashes are more practical for multiple oral erosions
- Topical calcineurin inhibitors (e.g. tacrolimus 0.1% ointment) and topical cyclosporine swish and spit may be beneficial
- Candida infection is a common occurrence in patients with mucosal pemphigus who are treated with systemic glucocorticoids. Oral nystatin swish and swallow/spit can be given as prophylaxis. Alternatively, patients can be monitored closely for the development of oropharyngeal candida infection and treatment instituted if infection develops.
- Dietary advice: soft diet, avoidance of spicy/very hot foods

- Maintenance of good oral hygiene: antiseptic mouthwashes (e.g. chlorhexidine 0.2% gluconate), teeth should be brushed twice daily with a soft-bristle brush and a bland toothpaste, flossing daily, regular dental consultations
- Nutritional management with the help of a dietician or a nutritionist if malnutrition is related to oral involvement

Patient consent

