Annex 1 Pemphigus disease area index (PDAI)

Skin	Activity	Damage
Anatomical location	Erosion/Blisters or new erythema	Post-inflammatory hyperpigmentation or erythema from resolving lesion
	0 absent 1 1–3 lesions, up to one >2 cm in any diameter, none > 6 cm 2 2–3 lesions, at least two > 2 cm diameter, none > 6cm 3 >3 lesions, none > 6 cm diameter 5 >3 lesions, and/or at least one >6 cm 10 >3 lesions, and/or at least one lesion >16 cm diameter or entire area	Number lesions if ≤ 3 0 absent 1 present
Ears		
Nose		
Rest of the face		
Neck		
Chest		
Abdomen		
Back, buttocks		
Arms		
Hands		
Legs		
Feet		
Genitals		
Total skin	/120	/12

Scalp	Activity	Damage
Scalp	Erosion/Blisters or new erythema	Post-inflammatory hyperpigmentation or erythema from resolving lesion
	0 absent 1 in one quadrant 2 two quadrants 3 three quadrants 4 affects whole skull 10 at least one lesion > 6 cm	Number lesions if ≤ 3 0 absent 1 present
Total Scalp (0–10)	/10	/1

Mucous membrane	Activity	Damage
Anatomical Location	Erosion/Blisters	Number lesions if ≤ 3
	0 absent 1 1 lesion 2 2–3 lesions 5 >3 lesions or 2 lesions >2 cm 10 entire area	
Eyes		
Nose		
Buccal mucosa		
Hard palate		
Soft palate		
Upper gingiva		
Lower gingiva		
Tongue		
Floor of mouth		
Labial bucosa		
Posterior pharynx		
Anogenital		
Total Mucosa	/120	

Total Activity Score:

Total Damage Score

Additional notes:

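### The aim and hypothesis ask what IVIG adds, but the arms also differ in rituximab calendar, so a result can be credited only to the whole regimens

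*Protocol*

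**What the plan says.** The Protocol's introductory paragraph says of the IVIG and rituximab combination that "whether it poses any benefit over rituximab alone, or with other more conventional immunosuppressive agents, has not been established". The aim that follows is to evaluate "early use of rituximab with or without IVIG in patients with moderate to severe pemphigus using protocols that were similar to those previously published", and to weigh the costs and benefits of the two arms. The Hypothesis section then states that "IVIg in combination with Rituximab is more superior than Rituximab alone in the treatment of moderate to severe pemphigus".

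The Methods section sets out two arms, randomised 1:1, with rituximab at the same per-dose amount (375 mg/m²) in each.

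- **Arm 1.** The bullets give 4-week courses from baseline and from week 24, and a third course described as "BSA weekly for 4 weeks at week 52". They sum up: "A total of 12 doses of rituximab will be given in 55 weeks". The table below the bullets splits the last four doses differently, placing two at weeks 52-53 and two at weeks 76-77.
- **Arm 2.** Rituximab is weekly in weeks 1-8, then at weeks 12, 16, 20 and 24, with IVIG. The summary for this phase is: "Thus in 24 week period patients received a total of 12 infusions of rituximab and 7 infusions of IVIG". Five further IVIG infusions, at weeks 30 to 76, are planned for patients clear of disease at the end of week 24, which leads to the overall statement "A total of 12 doses of rituximab will be given and 12 cycles of IVIG will be given".

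The Protocol does not mention that the rituximab calendars differ, or say how that bears on the interpretation of a result.

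**The concern.** A reader takes the hypothesis and aim as a question about one added component: give rituximab to everyone, add IVIG for half, and see what IVIG contributes. The arms do not isolate that component. Assignment to Arm 2 brings IVIG and a compressed rituximab calendar together, and assignment to Arm 1 brings neither.

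What is at stake is what the trial may conclude. If Arm 2 does better on relapse-free complete remission or time to initial remission, the hypothesis as worded would report a benefit of IVIG and feed it into the argument about IVIG's cost. If the arms look alike, it would report that IVIG adds nothing, although Arm 1 is still receiving scheduled rituximab long after Arm 2 has stopped. Neither statement would follow from the comparison made.

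**Working it through.** **Inputs** (Protocol, Methods, bullets and tables of each arm; scheduled doses only).

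- Arm 1, bullets: weeks 0, 1, 2, 3, 24, 25, 26, 27, 52, 53, 54, 55.
- Arm 1, table: weeks 0, 1, 2, 3, 24, 25, 26, 27, 52, 53, 76, 77.
- Arm 2: weeks 1 to 8, then 12, 16, 20, 24.
- Arm 2 IVIG: weeks 0, 4, 8, 12, 16, 20, 24, then 30, 38, 48, 60, 76.

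**Step 1: the Protocol's own totals.** Arm 1: 4 + 4 + 4 = 12 (bullets), or 4 + 4 + 2 + 2 = 12 (table). Arm 2: 8 + 4 = 12. IVIG: 7 + 5 = 12. All stated totals reproduce. The last scheduled rituximab dose is at week 55 or week 77 in Arm 1, and at week 24 in Arm 2.

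**Step 2: cumulative scheduled rituximab doses.**

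| Through week | Arm 1 | Arm 2 | Ratio, Arm 2 / Arm 1 |
|---|---|---|---|
| 3 | 4 | 3 | 0.75 |
| 8 | 4 | 8 | 2.0 |
| 23 | 4 | 11 | 2.75 |
| 24 | 5 | 12 | 2.4 |
| 27 | 8 | 12 | 1.5 |
| 52 | 9 | 12 | 1.33 |
| 55 | 12 (bullets) or 10 (table) | 12 | 1.0 or 1.2 |
| 77 | 12 | 12 | 1.0 |

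**Step 3: average timing.** The mean scheduled dose week is the sum of the dose weeks divided by 12.

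- Arm 1, bullets: (6 + 102 + 214) / 12 = 322 / 12 = 26.8.
- Arm 1, table: (6 + 102 + 105 + 153) / 12 = 366 / 12 = 30.5.
- Arm 2: (36 + 72) / 12 = 108 / 12 = 9.0.

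The longest gap between scheduled doses is 52 − 27 = 25 weeks in Arm 1 under either version, and 4 weeks in Arm 2.

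**Step 4: what the comparison can estimate.** Let I = 1 if assigned IVIG and C = 1 if assigned the compressed rituximab calendar. Write the expected outcome as a + b·I + c·C + d·I·C. Arm 1 has I = 0 and C = 0; Arm 2 has I = 1 and C = 1. The difference between arms is therefore b + c + d. There is one contrast for three terms, and no arm with I = 0 and C = 1 from which c could be learned. Randomisation makes b + c + d a fair estimate of the regimen difference but does not split it. A larger sample narrows the interval around the sum only, and no later analysis plan can recover b.

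**Step 5: after week 24.** On schedule, Arm 1 still has 12 − 5 = 7 rituximab doses to come and Arm 2 has none, while Arm 2 patients clear of disease have up to five IVIG infusions left. The calendars therefore stay different in the maintenance phase, now with rituximab on the Arm 1 side. That is why a null result is no easier to attribute to IVIG than a positive one.

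**The case against.** The strongest reply is that this is meant as a comparison of two published regimens. The aim says the regimens resemble previously published ones, cost and benefit are to be assessed for both arms, and the hypothesis names two treatments without saying that any difference is due to IVIG. Much of this stands. The design can make that comparison, costs included, and a reader might wrongly infer that the trial answers nothing. But the aim and hypothesis label the contrast as presence or absence of IVIG, and the Protocol does not acknowledge the calendar difference.

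It is also fair that the dose counts describe the schedule only. Further courses are allowed for relapse, and also if complete remission is not reached 2 months after the last rituximab dose. In Arm 1 that point falls at about week 3 + 8 to 9 = week 11 to 12. A patient treated then could have 4 + 4 + 1 = 9 doses through week 24, against 12 scheduled in Arm 2, a ratio of 1.33 and not 2.4. The primary outcome is also not stated as a week-24 endpoint, and scheduled totals do equalise by week 55 or 77. This limits how much weight the early counts can bear. It does not undo the aliasing, because rescue depends on response and the assigned calendars still differ.

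Two stronger readings are tempting and should be resisted.

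- The Additional notes cite a patient treated with rituximab alone as "8 doses weekly then 4 doses monthly – total 12 doses in 6/12", which resembles the Arm 2 calendar. A reader might infer that compressed rituximab by itself brings faster remission. It is one uncontrolled patient, treated without systemic steroid, with remission at 6 weeks and no comparison with a 4-dose course. It does not support that inference, and the point does not need it.
- Because B-cell and desmoglein samples fall at different intervals since the last rituximab dose, one might require tabulation by that interval. That is an optional analysis-plan detail. It would compare the arms at different times from randomisation, and differing intervals are inherent in comparing regimens.

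Finally, the Protocol calls this a pilot with about 20 patients. It still states a superiority hypothesis and tests at a two-sided 0.05 level, so the attribution matters.

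**Conclusion.** The point holds in this form: IVIG and rituximab timing are completely aliased, so the trial can compare two regimens but cannot attribute a difference, or its absence, to IVIG. Scheduled exposure differs by a factor of 2 to 2.75 between weeks 8 and 23 and by 2.4 through week 24, before rescue. Totals are equal only from week 55 (Arm 1 bullets) or week 77 (Arm 1 table).

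The conclusion rests on the assigned schedules alone and is the same under either version of the Arm 1 calendar. It needs no assumption that the calendar affects outcome, only that the documents do not rule this out. A reader might go further and infer that a win for Arm 2 would really be a rituximab effect, or that the bias favours Arm 2. The documents do not support that: neither the direction nor the size of any bias can be known from them.

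**What to change.** - Restate the hypothesis and aim as a comparison of two whole regimens: rituximab in separated courses versus front-loaded rituximab plus IVIG.
- Add a sentence on permitted conclusions: a difference or a null result, including the cost-benefit finding, applies to the regimens as given and not to IVIG as such.
- Reconcile the Arm 1 bullets and table, which disagree on the last four rituximab doses.

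Whether the two rituximab calendars should be aligned is a clinical decision for the sponsor. If they are not, the IVIG-specific wording should go.

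The cost is a few lines of Protocol text, with no extra patients, visits or data. The downside is a narrower claim than the present hypothesis makes.
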